## Appendix 8: WMA Declaration of Helsinki

### **WORLD MEDICAL ASSOCIATION DECLARATION OF HELSINKI**

#### **Recommendations guiding physicians in biomedical research involving human subjects**

Adopted by the 18th World Medical Assembly

Helsinki, Finland, June 1964

and amended by the

29th World Medical Assembly, Tokyo, Japan, October 1975

35th World Medical Assembly, Venice, Italy, October 1983

41st World Medical Assembly, Hong Kong, September 1989

and the

48th General Assembly, Somerset West, Republic of South Africa, October 1996

### **INTRODUCTION**

It is the mission of the physician to safeguard the health of the people. His or her knowledge and conscience are dedicated to the fulfilment of this mission.

The Declaration of Geneva of the World Medical Association binds the physician with the words, "The Health of my patient will be my first consideration," and the International Code of Medical Ethics declares that, "A physician shall act only in the patient's interest when providing medical care which might have the effect of weakening the physical and mental condition of the patient."

The purpose of biomedical research involving human subjects must be to improve diagnostic, therapeutic and prophylactic procedures and the understanding of the aetiology and pathogenesis of disease.

In current medical practice most diagnostic, therapeutic or prophylactic procedures involve hazards. This applies especially to biomedical research.

Medical progress is based on research which ultimately must rest in part on experimentation involving human subjects.

In the field of biomedical research a fundamental distinction must be recognized between medical research in which the aim is essentially diagnostic or therapeutic for a patient, and medical research, the essential object of which is purely scientific and without implying direct diagnostic or therapeutic value to the person subjected to the research.

Special caution must be exercised in the conduct of research which may affect the environment, and the welfare of animals used for research must be respected.

Because it is essential that the results of laboratory experiments be applied to human beings to further scientific knowledge and to help suffering humanity, the World Medical Association has prepared the following recommendations as a guide to every physician in biomedical research involving human subjects. They should be kept under review in the future. It must be stressed that the standards as drafted are only a guide to physicians all over the world. Physicians are not relieved from criminal, civil and ethical responsibilities under the laws of their own countries.

### **I. BASIC PRINCIPLES**

1. Biomedical research involving human subjects must conform to generally accepted scientific principles and should be based on adequately performed laboratory and animal experimentation and on a thorough knowledge of the scientific literature.

2. The design and performance of each experimental procedure involving human subjects should be clearly formulated in an experimental protocol which should be transmitted for consideration, comment and guidance to a specially appointed committee independent of the Investigator and the sponsor provided that this independent committee is in conformity with the laws and regulations of the country in which the research experiment is performed.
3. Biomedical research involving human subjects should be conducted only by scientifically qualified persons and under the supervision of a clinically competent medical person. The responsibility for the human subject must always rest with a medically qualified person and never rest on the subject of the research, even though the subject has given his or her consent.
4. Biomedical research involving human subjects cannot legitimately be carried out unless the importance of the objective is in proportion to the inherent risk to the subject.
5. Every biomedical research project involving human subjects should be preceded by careful assessment of predictable risks in comparison with foreseeable benefits to the subject or to others. Concern for the interests of the subject must always prevail over the interests of science and society.
6. The right of the research subject to safeguard his or her integrity must always be respected. Every precaution should be taken to respect the privacy of the subject and to minimize the impact of the study on the subject's physical and mental integrity and on the personality of the subject.
7. Physicians should abstain from engaging in research projects involving human subjects unless they are satisfied that the hazards involved are believed to be predictable. Physicians should cease any investigation if the hazards are found to outweigh the potential benefits.
8. In publication of the results of his or her research, the physician is obliged to preserve the accuracy of the results. Reports of experimentation not in accordance with the principles laid down in this Declaration should not be accepted for publication.
9. In any research on human beings, each potential subject must be adequately informed of the aims, methods, anticipated benefits and potential hazards of the study and the discomfort it may entail. He or she should be informed that he or she is at liberty to abstain from participation in the study and that he or she is free to withdraw his or her consent to participation at any time. The physician should then obtain the subject's freely-given informed consent, preferably in writing.
10. When obtaining informed consent for the research project the physician should be particularly cautious if the subject is in a dependent relationship to him or her or may consent under duress. In that case the informed consent should be obtained by a physician who is not engaged in the investigation and who is completely independent of this official relationship.
11. In case of legal incompetence, informed consent should be obtained from the legal guardian in accordance with national legislation. Where physical or mental incapacity makes it impossible to obtain informed consent, or when the subject is a minor, permission from the responsible relative replaces that of the subject in accordance with national legislation. Whenever the minor child is in fact able to give consent, the minor's consent must be obtained in addition to the consent of the minor's legal guardian.

12. The research protocol should always contain a statement of the ethical considerations involved and should indicate that the principles enunciated in the present Declaration are complied with.

## **II. MEDICAL RESEARCH COMBINED WITH PROFESSIONAL CARE (Clinical Research)**

1. In the treatment of the sick person, the physician must be free to use a new diagnostic and therapeutic measure, if in his or her judgement it offers hope of saving life, re-establishing health or alleviating suffering.
2. The potential benefits, hazards and discomfort of a new method should be weighed against the advantages of the best current diagnostic and therapeutic methods.
3. In any medical study, every patient - including those of a control group, if any - should be assured of the best proven diagnostic and therapeutic method. This does not exclude the use of inert placebo in studies where no proven diagnostic or therapeutic method exists.
4. The refusal of the patient to participate in a study must never interfere with the physician-patient relationship.
5. If the physician considers it essential not to obtain informed consent, the specific reasons for this proposal should be stated in the experimental protocol for transmission to the independent committee (I, 2).
6. The physician can combine medical research with professional care, the objective being the acquisition of new medical knowledge, only to the extent that medical research is justified by its potential diagnostic or therapeutic value for the patient.

## **III. NON-THERAPEUTIC BIOMEDICAL RESEARCH INVOLVING HUMAN SUBJECTS (Non-Clinical Biomedical Research)**

1. In the purely scientific application of medical research carried out on a human being, it is the duty of the physician to remain the protector of the life and health of that person on whom biomedical research is being carried out.
2. The subject should be volunteers - either healthy persons or patients for whom the experimental design is not related to the patient's illness.
3. The Investigator or the investigating team should discontinue the research if in his/her or their judgement it may, if continued, be harmful to the individual.
4. In research on man, the interest of science and society should never take precedence over considerations related to the wellbeing of the subject.

**Document Control Sheet**

Statistical Analysis Plan version & date:	Reason for update:	To match protocol version & date:
0.1, 12-Sep-2016	Initial creation	2.0a, 07-Jun-2016
0.2, 19-Oct-2016	Revision after LB comments	2.0a, 07-Jun-2016
1.0, 19-Oct-2016	Initial release	2.0a, 07-Jun-2016
2.0, 18-May-2017	Created "Rules of Inference" section. Refined outcome definition in protocol and SAP.	4.0
3.0, 10-Apr-2018	
Clarified intention to publish primary outcomes before the longer term secondary outcomes.
 
Clarified that the co-primary DCB outcome is treated as success if: CR or PR or SD is measured at or after the second scheduled CT scan; and the scan date is at least 16 weeks from registration. The second scan is scheduled at 18 weeks but frequently these are conducted slightly early for reasons outside the control of the trials unit. The third scheduled scan is not until 27 weeks.
 
Clarified that PD-L1 scores expressed as a range are interpreted as the midpoint, e.g. 10-20% is interpreted as PD-L1 = 15%.
 
Added hierarchical model as a proposed supplementary method of analysing primary outcomes. The described BEBOP method requires that baseline covariates be present. This assumption became pertinent when we allowed PD-L1-assay failures to register. The hierarchical
	5.0, 14-Aug-2017

	
method does not mandate covariates be present.
 
Added spider plot to specified graphical methods.
	
4.0, 18-Jun-2018	
Clarified the analysis method for DOR and DSD, and minor typographical changes.
	6.0
5.0, 31-Jan-2019	
Added prose describing the prior predictive event distributions of DCB and toxicity.
 
Removed the proposal of a hierarchical analysis. This was proposed to include patients with missing covariate data, because “missing” could be included as another variable level whilst providing some shrinkage to avoid overfitting the relatively small group. However, the inherent exchangeability assumption is not appropriate. We added instead a method that will use the original proposed BEBOP model and multiply-impute missing covariates.
 
Added plans to impute sum of target lesions when it is not reported but a RECIST response with respect to target lesions is reported, and vice versa.
 
Clarified some minor points.
 
Updated storage locations of snapshots, analyses, etc.
	6.0, 10-Jul-2018

## 1. INTRODUCTION

Please refer to the protocol for an introduction to non-small-cell lung cancer (NSCLC) and pembrolizumab.

### 1.1 Purpose of the Statistical Analysis Plan

This Statistical Analysis Plan (SAP) provides guidelines for the analysis and presentation of results for the PePS2 trial. This plan, along with all other documents relating to the analysis of this trial, will be stored in the 'Statistical Documentation' section of the Trial Master File. The statistical analysis will be carried out by the Trial Statistician.

---

## 1.2 Trial Synopsis

### Title

PePS2: A phase II trial of pembrolizumab in patients with non-small cell lung cancer and a performance status of 2

### Trial Design

Multi-centre, single-arm phase II trial, testing pembrolizumab in a population of patients with non-small cell lung cancer (NSCLC) and an Eastern Cooperative Oncology Group (ECOG) performance status of 2.

### Trial Objectives

This is a phase II trial of programmed cell death protein 1 (PD-1) blockade in patients with programmed death ligand 1 (PD-L1) defined NSCLC and an ECOG performance status of 2 with the primary purposes:

- To determine that pembrolizumab is safe and tolerable at the selected dose
- To detect the durable clinical benefit in this population of patients treated with pembrolizumab that would justify further investigation.

Secondary objective:

- To measure patient health related quality of life (HRQoL)

Exploratory objective:

- To discover possible biomarkers to predict for a response to pembrolizumab.

### Outcome Measures

Primary outcome measures

- Toxicity, defined as the occurrence of a treatment-related dose delay or treatment discontinuation due to an adverse event
- Durable clinical benefit (DCB), defined as the occurrence of a complete response (CR), partial response (PR) or stable disease (SD) without prior progressive disease (PD) at or after the second scheduled CT scan (scheduled in the protocol to occur at 18 weeks).

Secondary outcome measures:

- Objective response (OR)
- Progression-free survival time (PFS)
- Time to progression (TTP)
- Overall survival time (OS)
- Health related quality of life (HRQoL)
- Duration of objective response (DOR) and duration of stable disease (DSD).

### Sample Size

60 patients

### Patient Population

Patients with non-small cell lung cancer and an ECOG performance status of 2. Analysis of response will be stratified by PD-L1 proportion score and pre-treatment status in order to assess the rate of response in each cohort. Please refer to protocol for full inclusion and exclusion criteria.

---

## 2. TIMING AND REPORTING OF INTERIM AND FINAL ANALYSES

Interim analyses of primary outcomes and safety data will be presented at annual trial steering committee (TSC) meetings. There are no formal stopping rules defined.

The primary outcome will be submitted for publication within 6 months of the resolution of both co-primary outcomes for all patients. Available data on secondary outcomes may be included. A further publication may be required to report the full information on all non-primary outcomes. This will be submitted 12 months of the last patient completing treatment.

## 3. RECRUITMENT AND RANDOMISATION

### 3.1 Recruitment

We will report:

- The number of patients registered, summarised by site;
- The date the snapshot was taken;

### 3.2 Ineligible Patients

Ineligible patients are defined as those registered patients who are subsequently found to not meet the protocol eligibility criteria.

The statistician will report:

- The number of ineligible patients, and reasons for their ineligibility.

The primary analysis will include those patients found to be ineligible but a sensitivity analysis may be conducted and reported if the number of ineligible patients is substantial. Protocol deviations relating to treatment will be reported as part of treatment compliance (Section 7).

## 4. DATA QUALITY

The length of patient follow-up will be estimated using a reverse Kaplan-Meier curve.

The statistician will report:

- Median (95% CI) follow-up;
- The number of patients with disease response assessments at each assessment time.

## 5. ANALYSIS POPULATIONS

The *registered population* will be the set of all patients registered to the trial.

The general *analysis population* will be the set of all patients that received pembrolizumab.

### 5.1 Baseline Patient Characteristics

The statistician will report summary values (with appropriate measures of distribution) for patient characteristics including:

- Sex
- Age
- Number and type of previous therapies

---

- PD-L1 proportion score

The registered population will be used.

## 6. TREATMENT RECEIVED

The statistician will report:

- The number of patients starting treatment;
- The number of registered patients not starting treatment, plus reasons;
- The median (and range) number of cycles administered;
- The median (and range) time from registration to first treatment;
- The number of patients (%) in which treatment delays occurred, plus reasons;
- The number of patients (%) in which dose reduction occurred, plus reasons;

Treatment will be given every three weeks. A reported administered dose greater than zero will be taken to be a cycle of treatment. The registered population will be used.

## 7. DEVIATIONS

The statistician will report:

- The number of patients (%) who deviate from protocol and the different types of deviation

## 8. TOXICITY AND SAFETY ANALYSIS

Adverse events will be recorded according to CTCAE v.4.0.

In addition to the analysis of the toxicity primary outcome, the statistician will report:

- The number (and %) of patients experiencing at least one any grade adverse event and adverse reaction (i.e. considered at least possibly related to pembrolizumab);
- The number (and %) of patients experiencing at least one grade 3-4 adverse event and adverse reaction (i.e. considered at least possibly related to pembrolizumab);
- The incidence of each adverse event and adverse reaction (all grades and grade 3-4) as a per-patient rate;
- The number of deaths considered to be associated with pembrolizumab;
- The number (and %) of patients experiencing at least one serious adverse event (SAE).

Additionally, we may present summaries of adverse events for those that are and are not immune-related.

The analysis population will be used.

Note: Adverse Events experienced within a Serious Adverse Event will be included in the AE and AR reporting.

## 9. ANALYSIS

### 9.1 Definition and Calculation of Outcome Measures

#### 9.1.1 Primary Outcomes

The trial design is based on two co-primary outcome measures, toxicity and durable clinical benefit (DCB).

#### Toxicity

---

---

The toxicity co-primary outcome measure for the trial is defined as the occurrence of a treatment-related dose delay or treatment discontinuation due to an adverse event.

## DCB

Patients are scheduled to have CT scans every 9 weeks from baseline until disease progression. On each occasion, overall tumour burden will be assessed using RECIST 1.1, according to the study protocol. DCB is defined as the occurrence of CR, PR or SD without prior PD at or after the second scheduled CT scan. The second scan is scheduled to occur at the end of treatment cycle 6 at 18 weeks. For many reasons, scans often do not take place on the desired date. The exact timing of scans is largely out of the control of the trials office. The third scheduled scan is at 27 weeks. In NSCLC, disease status could easily change during the intervening 9 weeks. When calculating DCB, we include scans that occurred at least 16 weeks after registration.

For example, a disease response of (CR / PR / SD) at the first scheduled scan at 9 weeks, followed by a disease response of (CR / PR / SD) at the second scheduled scan at 16+ weeks would constitute DCB. Likewise, (CR / PR / SD) at 9 weeks, missing data at 18 weeks, and (CR / PR / SD) at the third scheduled scan at 27 weeks would also constitute DCB.

Patients for whom the DCB outcome could not be determined will be taken to be non-responders.

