Subjects who, on the assessment by the Investigator, require the use of any of the aforementioned treatments for clinical management should be withdrawn from the trial. Subjects may receive other medications that the Investigator deems to be medically necessary.

There are no prohibited therapies during the post-treatment follow-up phase.

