### 7.11 Patient Withdrawal

The Investigator will make every reasonable effort to keep each patient on trial. However, if the Investigator removes a patient from the trial treatment or if (s)he declines further participation final assessments will be performed, if possible. All the results of the evaluations and observations, together with a description of the reasons for trial withdrawal, must be recorded in the CRF. For patients withdrawing from trial treatment for reasons other than withdrawal of consent or due to disease progression then continue with RECIST 1.1 scans until documented progression as per protocol. For patients who have come off treatment due to unacceptable toxicity, CT scans will be performed every 9 weeks until disease progression or until the patient starts another anti-cancer treatment. CT scans are to be reported according to RECIST v1.1 criteria (see Appendix 2).

Following assessment by the Principal Investigator and discussion with the PePS2 Trial Office, patients who meet RECIST criteria for progressive disease (PD) may be continued on trial treatment if the treatment is tolerable and believed to be of clinical benefit. Documentation of continued clinical benefit should be recorded in the patient's medical notes by an Investigator.

In the event of a patient's decision to withdraw from the trial, the Investigator must ascertain from which aspects of the trial the patient wishes to withdraw, and record the details on the Withdrawal CRF. All patients will continue to be followed-up, and all information and tissue samples collected up until the point of withdrawal, will be retained and analysed.

Patients who withdraw from the trial due to AEs (clinical or laboratory) will be treated and followed according to accepted medical practice. All pertinent information concerning the outcome of such treatment must be recorded in the CRF.

The following are justifiable reasons for the Investigator to withdraw a patient from trial:

- Unacceptable toxicity
- Unforeseen events: any event which in the judgement of the Investigator makes further treatment inadvisable
- SAE requiring discontinuation of treatment
- Withdrawal of consent
- Serious violation of the trial protocol (including persistent patient attendance failure and persistent non-compliance)
- Withdrawal by the Investigator for clinical reasons not related to the trial drug treatment

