### 9.1.2 Secondary Outcomes

#### 9.1.2.1. Objective Response (OR)

Best overall response is the best response recorded over the whole period of assessment and could be complete response (CR), partial response (PR), stable disease (SD), progressive disease (PD) or inevaluable for response (NA, for which reasons such as early death due to disease or early death due to toxicity will be specified). Objective Response (OR) is the occurrence of CR or PR as best overall response. Objective Response will be based on responses confirmed using the subsequent 9-weekly scan but objective response based on unconfirmed responses will also be reported.

Furthermore, the number (and %) of patients in each best response category will be reported.

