#### 9.1.2.4. Progression-Free Survival Time (PFS)

This is defined as the time from commencement of trial treatment to the date of CT scan when progressive disease first recorded or date of death without previously recorded progression. Patients who are alive with no recorded progression at the time of analysis will be censored at the date of the CT scan when they were last recorded with an evaluable measure that was not progression.

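### The DCB and OR definitions do not exclude scans taken after a new systemic anti-cancer treatment started before progression, so disease control on another drug can be scored as pembrolizumab efficacy

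*SAP*

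**What the plan says.** **Outcome definitions.** SAP 9.1.1 states: "DCB is defined as the occurrence of CR, PR or SD without prior PD at or after the second scheduled CT scan". On timing it adds: "When calculating DCB, we include scans that occurred at least 16 weeks after registration". There is no upper time limit and no requirement that the patient is still on pembrolizumab. Undetermined outcomes are failures: "Patients for whom the DCB outcome could not be determined will be taken to be non-responders". For OR, SAP 9.1.2.1 says: "Best overall response is the best response recorded over the whole period of assessment". Protocol 13.1.1 and 13.1.2.1 define DCB and OR in the same way, without the 16-week clause. No efficacy definition in either document mentions a new anti-cancer treatment.

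**Later therapy.** Under Protocol 7.9.2, patients who "require the use of any of the aforementioned treatments for clinical management should be withdrawn from the trial". The same section then says: "There are no prohibited therapies during the post-treatment follow-up phase".

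**Scans after stopping.** The documents give three accounts:
- Protocol 7.11, for patients leaving treatment for reasons other than "withdrawal of consent or due to disease progression then continue with RECIST 1.1 scans until documented progression as per protocol". It adds that scans after a toxicity stop end at progression or at another anti-cancer treatment.
- Protocol Appendix 2 continues scans where possible for anyone who discontinues before progression, and names no stop at new therapy.
- Footnote 20 of the Schedule of Events requires follow-up scans only for patients who come off because of toxicity, until progression or another cancer treatment.

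**Recording of later therapy.** Footnote 23 of the Schedule of Events and Protocol 7.10 mention only treatment given after progression.

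**The concern.** DCB is meant to measure what pembrolizumab does. The trial has one arm, so no control group offsets disease control obtained on another drug. The decision is made cohort by cohort against a 10% efficacy hurdle, and cohorts 3 and 6 are expected to hold about 7 patients each (SAP Table 5).

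Consider a patient who stops pembrolizumab at week 6 because of symptomatic deterioration without objective progression, a category that Protocol Appendix 2 recognises. The patient starts another systemic treatment and has stable disease at week 18. If that scan is done and reported, every condition of the DCB definition is met. A partial response on that scan would also enter the unconfirmed OR, and the confirmed OR if the next 9-weekly scan agrees. So the rule as written can return a wrong classification; this goes beyond a missing detail.

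**Working it through.** **1. Who can be affected, by reason for stopping before progression.**
- *Toxicity:* scans end at the new treatment (footnote 20 and Protocol 7.11 agree). A patient who switches without a qualifying scan becomes non-DCB under the existing non-responder rule. Normally no miscredit.
- *Consent withdrawal:* outside the continued-scan sentence in 7.11.
- *Other reasons,* such as symptomatic deterioration or need for a prohibited therapy: 7.11 and Appendix 2 point to continued scans with no stop at new therapy; footnote 20 requires none. Miscredit is possible if scans are done.
- *Radiotherapy while on trial:* 7.9.2 may allow it to a solitary symptomatic lesion or the brain. No outcome definition says how it is handled.

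**2. Size of one event.** 1/60 = 1.7 percentage points on the overall DCB rate; 1/7 = 14.3 points in a cohort of 7.

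**3. Reproducing the plan's figures.** The SAP 9.3.2 design was simulated with Dirichlet-multinomial cohort sizes, n = 60, the Table 3 priors, no efficacy-toxicity association and 2,000 trials per setting. Approval probabilities for Table 6, scenario 5, cohorts 1 to 6:
- SAP: 0.234 / 0.460 / 0.800 / 0.232 / 0.445 / 0.758
- Check: 0.230 / 0.473 / 0.816 / 0.234 / 0.440 / 0.770

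All agree within 2 points.

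**4. Effect on a borderline dataset.** Model: logit(efficacy) = α + βx₁ + γx₂ + ζx₃ with the Table 3 priors, efficacy margin only. Cohort sizes 9/13/7/13/11/7 are close to the Table 5 means and sum to 60. The criterion is Pr(efficacy > 0.1) > 0.7.
- One DCB in each cohort: cohort 1 = 0.39, cohort 3 = 0.63, cohort 6 = 0.56. None passes.
- One extra DCB in cohort 3: cohort 3 = 0.86, passes.
- One extra in cohort 1: cohort 1 = 0.71 and cohort 3 = 0.72; both pass.
- One extra in cohort 6: cohort 6 = 0.83 and cohort 3 = 0.75; both pass.

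Because the model shares information, one patient can move two cohorts over the efficacy threshold. The toxicity criterion must still be met.

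**5. Effect away from the border.** With DCB counts near the scenario 8 means (2/2/4/1/2/3), cohort 3 is 1.000; with 3 DCBs there instead of 4 it is 0.997. Its decision does not change. In the same dataset cohort 4, at one DCB, goes from about 0.6 to about 0.8 with a second.

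**6. Sensitivity to frequency (assumed; the documents give no rate).** Let a fraction m of true DCB failures in every cohort be scored as DCB, so the apparent rate is p + m(1 − p). For p = 0.10 and m = 0.05 this is 0.10 + 0.05 × 0.90 = 0.145. Approval in scenario 5, cohort 1 (true DCB 10%):
- m = 0: 0.23
- m = 0.02: 0.31
- m = 0.05: 0.45
- m = 0.10: 0.64

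Using only scans before new therapy returns the m = 0 value.

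**The case against.** The strongest reply is that the route is narrow. It needs a stop without progression, toxicity or consent withdrawal, then a new systemic treatment, then a reported non-progression scan at 16 weeks or later. Footnote 20 would leave most such patients without required scans. Protocol 7.9.2 speaks of withdrawal from the trial, while the 7.11 scan sentence concerns withdrawal from trial treatment, so continued scanning of those patients is an inference. Inclusion criteria also require that all standard therapy judged appropriate has been completed, which may make switching less common. All of this stands and limits the expected frequency. It does not close the gap, because 7.11 and Appendix 2 point the other way.

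The dataset in step 4 was chosen at the border: 6 DCBs in 60 is the 10% hurdle itself. That is fair, and step 5 shows the contrast.

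Three stronger readings are tempting but not supported:
- *The error always favours pembrolizumab.* A toxicity leaver who switches before a qualifying scan already counts as a failure.
- *PFS is seriously inflated.* A death after a switch is an event at its own date ("or date of death without previously recorded progression"), so time on the other drug is included, but living patients are censored at their last non-progression scan. Assuming 3 to 10 of 60 patients stop for toxicity and switch before progression, with median PFS 4 months and median progression-to-death 5 months, simulated 12-month PFS rises from 16.3% to between 17.4% and 19.5%, that is by 1.1 to 3.2 points. The 90% half-width is about 1.645 × √(0.163 × 0.837/60) = 7.8 points. The upper assumption of 10 exceeds all 6 toxicity events expected at a 10% rate. Counting such deaths is a defensible choice of estimand.
- *Pre-progression switches go undated.* Protocol 7.9.1 records concomitant medication to 30 days after the last dose. The gap is switches after that and before progression.

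**Conclusion.** The point holds for DCB and OR, in patients who stop pembrolizumab before progression for reasons other than toxicity or consent withdrawal and who are still scanned. For them the written rules can credit another drug's effect to pembrolizumab. One such patient can reverse the efficacy criterion in a borderline cohort (0.63 to 0.86 in cohort 3 in the example) but not in a clearly effective one. How often this would happen cannot be judged from the documents, and depends partly on which of the conflicting scan instructions sites follow. The posterior figures rest on the SAP priors, the stated cohort sizes and counts, and an ignored association term; the misattribution rates are assumptions. This is a cheap improvement, not a must-fix. It is best settled before the primary analysis, so that nobody has to decide case by case with outcomes known.

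**What to change.** 1. In SAP 9.1.1 and 9.1.2.1 and Protocol 13.1, count for DCB and OR only scans before the start of any new systemic anti-cancer treatment. A patient with no qualifying scan before that date is non-DCB under the existing non-responder rule.
2. State in the outcome definitions how permitted on-trial radiotherapy is handled.
3. Reconcile footnote 20 of the Schedule of Events with Protocol 7.11 and Appendix 2.
4. In footnote 23 and Protocol 7.10, record any new anti-cancer treatment with its start date, whether before or after progression.
5. Keep the current PFS, DOR and DSD definitions. Add, as a sensitivity analysis only, censoring at the last evaluable scan before new therapy.

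The cost is a few sentences and one date on the case report form. Sample size, priors and thresholds do not change. The DCB rate may come out slightly lower, and the sensitivity analysis loses a few events through censoring that may itself be informative.
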